3.5.2. Laboratory Data

Below is a list of clinical laboratory test parameters.

- Hematology: hemoglobin, hematocrit, red blood cell count, platelet count, white blood cell count (% and absolute), neutrophils, eosinophils, monocytes, basophils and lymphocytes.
- Chemistry: blood urea nitrogen/Urea, glucose, creatinine, sodium, potassium, chloride, Bicarbonate or Total CO₂, alanine aminotransferase, aspartate aminotransferase, total bilirubin, alkaline phosphatase, albumin, and total protein.

3.5.3. Physical Examinations

A physical examination includes, but not limited to the following organ or body systems; head, ears, eyes, nose, mouth, skin, heart and lung examinations, lymph nodes, musculoskeletal, abdomen (liver, spleen), and neurological systems. In addition, an assessment will be made of the condition of all AD-involved skin.

3.5.4. Vital Signs

Vital sign measurements are temperature, respiratory rate, pulse rate, and blood pressures.

4. ANALYSIS SETS

Population	Description
Full Analysis Set (FAS)	All subjects randomized and dispensed study drug, subjects are assigned to the randomized treatment regardless of what treatment was received.
Per Protocol Analysis Set (PPAS)	All subjects in the FAS who complete the Day 29 evaluation without any major protocol deviations.
Safety Analysis Set	All subjects who are randomized and received at least one confirmed dose of investigational product. The subject will be assigned to the randomized treatment group if he received at least one dose of the randomized treatment. The subject will be assigned to the other treatment group if he does not receive any of the randomized treatment.

Specifically, PPAS will include subjects in the FAS who meet all of the following criteria:

- Met all of the Inclusion Criteria and none of the Exclusion Criteria;
- Have not taken any prohibited concomitant medications during the treatment period;
- Completed the Day 29 Visit, including the Day 29 efficacy evaluation of EASI and ISGA, subjects ≥ 12 years who have missing Week 4 Peak Pruritus NRS evaluation will be excluded;
- Have applied 80%–120% of the total number of expected doses (56 doses) during the treatment period;
- Have not missed 6 or more consecutive doses during the treatment period;
- Were in the visit window (± 3 days) for the Day 29 Visit.

Subjects who prematurely discontinue from the study due to lack of efficacy or a treatment related TEAE will be placed back into PPAS.

Data for all participants will be assessed to determine if participants meet the criteria for inclusion in PPAS prior to unblinding and releasing the database and classifications will be documented per standard operating procedures.

5. GENERAL METHODOLOGY AND CONVENTIONS

The final analysis will be performed based on the final released data set after last subject last visit (LSLV).

5.1. Hypotheses and Decision Rules

The study will be declared a success with crisaborole shown to be superior to vehicle with respect to the primary efficacy endpoint, percent change from baseline in EASI total score at Day 29, if the mean percent change in the Crisaborole arm is lower than that in the vehicle arm and the difference is statistically significant at the two-sided level of 0.05.

After crisaborole is shown to be superior to vehicle with respect to the primary efficacy endpoint, it will be compared with vehicle with respect to the key secondary efficacy endpoints using gate-keeping method.

After and only after crisaborole is shown to be superior to vehicle with respect to the percent change from baseline in EASI total score at Day 29, crisaborole will be declared superior to vehicle with respect to the improvement rate in ISGA at Day 29, i.e., the percentage of patients with ISGA score of Clear (0) or Almost Clear (1), at Day 29, if the rate in the crisaborole arm is higher than that in the vehicle arm and the difference is statistically significant at the two-sided level of 0.05.

After and only after crisaborole is shown to be superior to vehicle with respect to the improvement rate in ISGA at Day 29, crisaborole will be declared superior to vehicle with respect to the success rate in ISGA at Day 29, i.e., the percentage of patients with ISGA score of Clear (0) or Almost Clear (1) with at least a 2 grade improvement from Baseline, at Day 29, if the rate in the crisaborole arms is higher than that in the vehicle arm and the difference is statistically significant at the two-sided level of 0.05.

After and only after crisaborole is shown to be superior to vehicle with respect to the success rate in ISGA at Day 29, crisaborole will be declared superior to vehicle with respect to the change from baseline in Peak Pruritus NRS at Week 4 - for subjects ≥ 12 years, if the mean change of the crisaborole arm is lower (i.e., larger reduction) than that in the vehicle arm and the difference is statistically significant at the two-sided level of 0.05.

5.2. General Methods

5.2.1. Analyses for Binary Endpoints

The binary endpoints will be descriptively summarized using sample size, number, percentage and 95% confidence interval (CI) of percentage at each time point.

Binary data will be analyzed by comparing response rates between treatment groups. Normal approximation to the difference in response rates will be used to obtain p-values and 95% CI.

5.2.2. Analyses for Continuous Endpoints

Continuous endpoints will be descriptively summarized using sample size, mean, standard deviation, median and range.

For the analysis in which missing values are not explicitly imputed, continuous endpoints will be analyzed using a linear Mixed effect Model for Repeated Measures (MMRM, [Mallinckrodt et al. 2001](#)) with treatment group, visit, and treatment group-by-visit interaction as factors and baseline value as a covariate. Within-subject variability will be accounted for using a random effect with the first-order autoregressive (AR(1)) covariance matrix if there are no convergence issues, otherwise other structures will be considered.

5.2.3. Analyses for Time-to-Event Endpoints

Time-to-event analysis will be used to analyze time-to-event data.

Kaplan-Meier (product limit) method will be used for estimation of proportion of participants with event, time-to-event curve, median (95% CI) time-to-event.

5.3. Methods to Manage Missing Data

Multiple Imputation based on Markov Chain Monte Carlo (MI-MCMC)

Missing ISGA scores will be derived for the analysis using the method of MCMC multiple imputation. Multiple imputation and subsequent analysis will involve the following four principal tasks:

1. Calculate the number of missing values to be imputed by MCMC (nmiss) for the Day 29 value.
2. Create a data set, one for each treatment group, of subjects with observed values and those needing imputation by MCMC. The missing ISGA values in each data set will be filled in using the MCMC method “10× nmiss” times to generate “10 × nmiss” data sets. The resulting data sets for each treatment group will be combined into one complete data set by imputation. The imputed values will be rounded to the nearest value of 0, 1, 2, 3, or 4.
3. For each complete data set, derive dichotomous variables Success in ISGA (Clear [0] or Almost Clear [1] with a 2-point change from Baseline) and Improvement in ISGA (Clear [0] or Almost Clear [1]). The estimated treatment effect and its standard error for each complete data set will be calculated with the method specified in [Section 5.2.1](#).
4. Combine the estimated treatment effects and standard errors from the above into a single inference using Rubin’s formulae as implemented in SAS PROC MIANALYZE.

Success in ISGA and Improvement in ISGA will be derived from the imputed complete ISGA data sets.

For EASI-50 and EASI-75, missing EASI total scores will be imputed in the same way as missing ISGA scores except no rounding will be done to the imputed values. Missing EASI-50 and EASI-75 values will be derived from the imputed complete EASI data sets.

Non-Responder Imputation (NRI) Non-Responder Imputation (NRI) as another alternative way of handling missing data will also be used in Supportive analyses. If a subject has missing data for a binary endpoint at a scheduled visit, this subject will be defined as a non-responder for that endpoint at that visit.

Repeated measure modeling with no explicit imputation For continuous endpoints, missing values are assumed missing at random (MAR) and will be handled by MMRM.

In general, for descriptive statistics and time to event analysis, missing values will not be imputed.

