4.1. Inclusion Criteria

Subjects must meet all of the following inclusion criteria to be eligible for enrollment into the study:

1. Is male or female and the appropriate age in years (2 years and older) at time of informed consent/assent.
2. Has a clinical diagnosis of AD according to the criteria of Hanifin and Rajka (See [Appendix 2](#)).
3. Has AD involvement of $\geq 5\%$ Treatable BSA (excluding the scalp) at Baseline/Day 1.
4. Has an ISGA score of Mild (2) or Moderate (3) (excluding the scalp) at Baseline/Day 1.
5. Has adequate venous access to permit venipuncture for clinical safety laboratory sampling.
6. Female subjects of childbearing potential who have a negative urine pregnancy test at the screening visit and negative urine pregnancy test at the baseline visit prior to randomization. A female is of childbearing potential if, in the opinion of the investigator, she is biologically capable of having Children (includes any female who has experienced menarche and does not meet the criteria for females not of childbearing potential. Female subjects of non-childbearing potential must meet at least 1 of the following criteria:
 - a. Achieved postmenopausal status, defined as follows: cessation of regular menses for at least 12 consecutive months with no alternative pathological or physiological cause; have a serum follicle stimulating hormone (FSH) level confirming the postmenopausal state;
 - b. Have undergone a documented hysterectomy and/or bilateral oophorectomy;
 - c. Have medically confirmed ovarian failure.
7. Evidence of a personally signed and dated informed consent/assent document indicating that the subject [or parent(s)/legal guardian] has been informed of all pertinent aspects of the study.
8. Willing and able to comply with scheduled visits, treatment plan, laboratory tests and other study procedures.

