9.2.2. Analysis of Key Secondary Endpoints

Type I error rate will be strictly controlled for the analyses of the key secondary efficacy endpoints with sequential testing in the following order: Improvement in ISGA (defined as ISGA score of Clear (0) or Almost Clear (1)) at Day 29, Success in ISGA (defined as an ISGA score of Clear (0) or Almost Clear (1) with at least a 2 grade improvement from Baseline) at Day 29, and change from baseline to Week 4 in weekly average of peak pruritus Numeric Rating Scale (NRS). The percentage of subjects with Improvement in ISGA at Day 29 will be compared between crisaborole arm and vehicle arm and the difference will be tested based on normal approximation to response rates. Missing Day 29 ISGA scores will be derived for the analysis using the method of multiple imputations (MI) based on Markov Chain Monte Carlo (MCMC).

The percentage of subjects with Success in ISGA at Day 29 will be analyzed in the same way as Improvement in ISGA. The same sets of imputed ISGA scores will be used for both Success in ISGA and Improvement in ISGA.

The change from baseline to Week 4 in weekly average of peak pruritus NRS will be analyzed using a linear mixed-effect model for repeated measures that includes treatment group, visit, and treatment -group by visit interaction as factors and baseline value as a covariate. Within-subject variability will be accounted for using a random effect with the first order autoregressive (AR(1)) covariance matrix.

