
 To evaluate the effect of crisaborole ointment, 2% applied BID versus Vehicle on additional efficacy endpoints in Chinese and Japanese pediatric and adult subjects (Ages 2 years and older) with mild to moderate AD. 	
 Achievement of Improvement in ISGA (defined as ISGA score of clear (0) or almost clear (1)) at Day 29. 	
The estimand is the hypothetical estimand, which estimates the effect if all participants maintain their randomized treatment and adhere to the protocol. It includes the following 5 attributes
 
 Treatment: Crisaborole Ointment 2% BID vs Vehicle Ointment BID. Population: Chinese and Japanese pediatric and adult subjects (ages 2 years and older) with mild to moderate AD as defined by the inclusion and exclusion criteria Variable: Improvement in ISGA at Day 29. Intercurrent events: Had patient not discontinued from treatment prior to Day 29.

Objectives	Endpoints	Estimands
		
 Population-level summary: Difference in percentage of subjects with Improvement in ISGA between crisaborole ointment 2% BID vs corresponding vehicle.
Secondary:	Secondary:	Secondary:

 To evaluate the effect of crisaborole ointment, 2% applied BID versus Vehicle on additional efficacy endpoints in Chinese and Japanese pediatric and adult subjects (Ages 2 years and older) with mild to moderate AD. 	
 Achievement of Success in ISGA (defined as an ISGA score of Clear (0) or Almost Clear (1) with at least a 2 grade improvement from Baseline) at Day 29. 	
The estimand is the hypothetical estimand, which estimates the effect if all participants maintain their randomized treatment and adhere to the protocol. It includes the following 5 attributes
 
 Treatment: Crisaborole Ointment 2% BID vs Vehicle Ointment BID. Population: Chinese and Japanese pediatric and adult subjects (ages 2 years and older) with mild to moderate AD as defined by the inclusion and exclusion criteria. Variable: Success in ISGA at Day 29. Intercurrent events: Had patient not discontinued from treatment prior to Day 29. Population-level summary: Difference in percentage of subjects with Success in ISGA between crisaborole ointment 2% BID vs corresponding vehicle.

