3.2. Secondary Endpoints

Efficacy endpoints:

- Key secondary efficacy endpoints
 - Achievement of Improvement in ISGA (defined as ISGA score of clear (0) or almost clear (1)) at Day 29.

- Achievement of Success in ISGA (defined as an ISGA score of Clear (0) or Almost Clear (1) with at least a 2 grade improvement from Baseline) at Day 29.
- Change from Baseline in Peak Pruritus Numeric Rating Scale (NRS) at Week 4 - for subjects ≥ 12 years.
- Other secondary efficacy endpoints
 - Success in ISGA (defined as an ISGA score of Clear (0) or Almost Clear (1) with at least a 2 grade improvement from Baseline) over time.
 - Improvement in ISGA (defined as ISGA score of clear (0) or almost clear (1)) over time.
 - Percent change from Baseline in EASI total score over time.
 - Change from Baseline in %BSA over time.
 - Achievement of EASI-50 ($\geq 50\%$ improvement from baseline) over time.
 - Achievement of EASI-75 ($\geq 75\%$ improvement from baseline) over time.
 - Change from baseline in Peak Pruritus NRS over time - for subjects ≥ 12 years.
 - Changes from baseline in Patient Reported Itch Severity Scale over time - for subjects ≥ 6 years and < 12 years.
 - Change from baseline in Observer Reported Itch Severity Scale over time - for subjects < 6 years.
 - DLQI, CDLQI, IDQOL, DFI, POEM, PGIS/OGIS, PGIC/OGIC over time.

CCI [REDACTED]

- [REDACTED]
- [REDACTED]
- [REDACTED]
- [REDACTED]

[REDACTED]

[REDACTED]

[REDACTED]

[REDACTED]

[REDACTED]

[REDACTED]

[REDACTED]

[REDACTED]

[REDACTED]

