6.2.2.1. Main Analysis

- Estimand strategy: Hypothetical.
- Analysis set: FAS. Participants with baseline ISGA score of Clear (0) or Almost Clear (1) will be excluded.
- Analysis methodology: The percentage of subjects achieving Success in ISGA at Day 29 will be compared between crisaborole arm and vehicle arm and the difference will be tested based on normal approximation to response rates.
- Intercurrent events and missing data: Data after treatment discontinuation prior to Day 29 will not be considered. Missing ISGA scores will be derived for the analysis using MI-MCMC.
- Reporting results:
 - Tables: The sample size, number, percentage and 95% CI of percentage of subjects achieving Success in ISGA at Day 29 will be presented for each treatment. Risk difference and the corresponding 95% CI and p-value for the test of difference based on normal approximation to response rates will also be presented at Day 29.

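### SAP 5.3 derives ISGA Success from a 2-point change rather than a minimum of two grades; read literally, it scores Moderate-to-Clear as a failure

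*SAP*

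**What the plan says.** SAP 5.3 sets out four steps for the multiple imputation of ISGA. Step 3 applies to each completed data set and tells the analyst to "derive dichotomous variables Success in ISGA (Clear [0] or Almost Clear [1] with a 2-point change from Baseline". The bracket gives neither a minimum nor a direction of change. The closing lines of the procedure say that both ISGA responder variables come from the completed data sets, so step 3 governs observed as well as imputed scores.

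The endpoint is worded differently elsewhere:

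- SAP 2.1: "Almost Clear (1) with at least a 2 grade improvement from Baseline) at Day 29".
- SAP 3.2: "with at least a 2 grade improvement from Baseline) at Day 29".
- SAP 5.1, decision rule: "Almost Clear (1) with at least a 2 grade improvement from Baseline, at Day 29".
- Protocol 9.2.2: "with at least a 2 grade improvement from Baseline) at Day 29, and change from baseline to Week 4". Protocol section 2 uses the same minimum.

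Protocol 4.1, criterion 4, limits entry by baseline severity: "Has an ISGA score of Mild (2) or Moderate (3"). For the Success analysis, SAP 6.2.2.1 adds: "Participants with baseline ISGA score of Clear (0) or Almost Clear (1) will be excluded".

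Success also has a place in the testing sequence. SAP 5.1 opens the Peak Pruritus NRS comparison "After and only after crisaborole is shown to be superior to vehicle with respect to the success rate in ISGA at Day 29".

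**The concern.** Step 3 is the only numbered programming instruction for this endpoint, and it does not match the definition it should implement. A programmer who codes the bracket as written would require a change equal to 2. A subject who goes from Moderate to Clear changes by 3 and would be counted as a failure, although that is the best outcome open to an eligible subject.

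The FAS main analysis (SAP 6.2.2.1) and the PPAS analysis (SAP 6.2.2.2) both use this imputation procedure. The over-time analysis (SAP 6.2.4) reaches step 3 only by cross-reference, because step 1 is written for the Day 29 value. Success is the second of three key secondary endpoints tested in fixed order, so a derivation error could affect both its own test and whether the Peak Pruritus NRS test is opened.

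**Working it through.** **Inputs.** Eligible baseline ISGA is 2 or 3 (protocol 4.1). Day 29 ISGA is an integer from 0 to 4, and imputed values are rounded to that scale (SAP 5.3, step 2). The planned arms are 256 and 128 (protocol 9.1).

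**Enumeration.** Two baselines by five Day 29 scores give 2 × 5 = 10 pairs. Six of them end at 2, 3 or 4 and fail under either wording. The other four are:

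| Baseline | Day 29 | Improvement | Minimum of 2 grades | Change equal to 2 |
|---|---|---|---|---|
| 2 | 1 | 1 | No | No |
| 2 | 0 | 2 | Success | Success |
| 3 | 1 | 2 | Success | Success |
| 3 | 0 | 3 | Success | **No** |

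The definition gives three Success transitions and the literal bracket gives two. The wordings disagree on 1 of 10 pairs, 3 to 0.

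**Direction.** Leaving out the direction has no effect. A worsening of 2 points starts at 0 or higher and ends at 2 or higher, so it can never finish at 0 or 1.

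**Size per subject.** For an observed 3-to-0 responder coded as a failure:

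- crisaborole: 1/256 = 0.39 percentage points
- vehicle: 1/128 = 0.78 percentage points

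A subject whose score is imputed is affected only in those imputations that give 0 from a baseline of 3, so the contribution is smaller.

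**Effect on the treatment difference.** This needs the share of Successes that are 3 to 0 in each arm, f_c (crisaborole) and f_v (vehicle), which the documents do not give. As an illustration, take the pooled Phase 3 response rates in protocol 9.1, 32.1% and 21.8%. The literal difference would be

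32.1(1 − f_c) − 21.8(1 − f_v) = 10.3 − 32.1 f_c + 21.8 f_v.

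- Assumed f = 0.10 in both arms: 28.9 − 19.6 = 9.3 points.
- Assumed f = 0.30 in both arms: 22.5 − 15.3 = 7.2 points.
- The difference would grow instead of shrink if f_v exceeded 32.1/21.8 = 1.47 times f_c.

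So even the direction of the effect is not determined by the documents.

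**The case against.** The strongest reply is that the definition is already settled. SAP section 3 is the section for endpoint definitions, and it, the decision rule and the protocol agree. SAP 5.3 deals with missing data, and step 3 attaches a short gloss to a variable defined elsewhere. The gloss does not say that the change must be exactly 2, and because it also omits direction it is plainly not meant as a full definition. This largely stands, and it is why the point is minor: the intention is clear and no method is in dispute. It does not justify leaving the text as it is, because this is the step a programmer will implement.

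A second reply is that a literal coding would probably show. The non-responder-imputation analysis in SAP 6.2.2.2 does not pass through step 3, so an observed 3-to-0 subject could be a failure in the main table and a success in the supportive one. That is a useful check, but it works only if someone compares the two tables, and it fails if both programs share the same derivation.

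A third reply is that the count of one disagreement holds for eligible subjects, not for the whole FAS. That is correct. SAP 6.2.2.1 removes only baselines 0 and 1, so a subject randomized in error at baseline 4 would stay in. For that subject 4 to 1 and 4 to 0 would also be lost under the literal reading. This adds to the mismatch and does not remove it.

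**Conclusion.** The concern holds as a minor inconsistency. As written, the derivation rule in SAP 5.3 contradicts the endpoint definition and the decision rule. For eligible subjects it would misclassify exactly one of the three Success transitions, 3 to 0.

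There is no effect if the program follows SAP 3.2 and 5.1. If it follows step 3 literally, the cost is 0.39 or 0.78 percentage points per observed 3-to-0 subject, depending on arm and assuming the planned 256:128. No effect on the treatment difference or on power is claimed, because the share of 3-to-0 responders is not given.

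**What to change.** In SAP 5.3 step 3, replace the two-point clause in the bracket with the threshold already used in SAP 3.2, so that two grades of improvement is a minimum. Make the change before unblinding. The documents do not show whether unblinding has taken place; if it has, confirm and record that the program applied the minimum to observed and imputed scores alike.

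Two editorial corrections can go into the same revision:

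- **SAP Appendix 3.2, Table 8.** The top area band stops short of 100%, so a fully involved region has no area score. Protocol Table 3 includes 100% in the band scored 6. Align the SAP table with it. Only a region exactly 100% involved is affected.
- **SAP 6.2.11.** The rule for one missing item sums nine remaining items for every questionnaire listed, including POEM. POEM has seven items (SAP Appendix 3.8), so 7 − 1 = 6 remain. Refer to the remaining non-missing items: nine for DLQI, CDLQI, IDQOL and DFI, and six for POEM. POEM is summarized descriptively only.

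The cost is three wording edits to the SAP. Data collection and statistical methods do not change.

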9.1. Sample Size Determination

The total sample size of 384 subjects in this study with a 2:1 randomization ratio (256:128) will provide approximately 90% power to detect a 12% difference of percent change from baseline in EASI total score at Day 29 between crisaborole arm and vehicle arm at the 0.05 (2-sided) significance level, CCI

Comparative EASI data relative to vehicle was not collected in previous crisaborole studies. The 12% treatment effect in EASI percent improvement was converted from the ISGA response in the Phase 3 studies using a linear regression equation that evaluated the relationship between ISGA response rate and EASI percent improvement from historical trial

data of other topical products (data on file). From the crisaborole Phase 3 pooled data, the ISGA response rate is 32.1 % for crisaborole and 21.8% for vehicle. The converted EASI percent improvement is 38.9% and 26.8% respectively. The difference of EASI percent improvement between crisaborole and vehicle is approximately 12%.

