Erythema (E)		
0	Absent	None; may have residual discoloration (post-inflammatory hyperpigmentation and/or hypopigmentation).
1	Mild	Light pink to light red
2	Moderate	Red
3	Severe	Deep, dark red
Induration/Papulation (I)		
0	Absent	None
1	Mild	Barely palpable to slight, but definite hard thickened skin and/or papules
2	Moderate	Easily palpable moderate hard thickened skin and/or papules
3	Severe	Severe hard thickened skin and/or papules
Excoriation (Ex)		
0	Absent	None
1	Mild	Slight, but definite linear or picked scratch marks or penetrating surface injury
2	Moderate	Moderate linear or picked scratch marks or penetrating surface injury
3	Severe	Severe linear or picked scratch marks or penetrating surface injury
Lichenification (L)		
0	Absent	None
1	Mild	Barely perceptible to slight, but definite thickened skin, fine skin markings, and lichenoid scale
2	Moderate	Moderate thickened skin, coarse skin markings, and coarse lichenoid scale
3	Severe	Severe thickened skin with very coarse skin markings and lichenoid scale

* The EASI will exclude scalp from the assessment/scoring

In each body region, the sum of the Clinical Signs Severity Scores for erythema, induration/papulation, excoriation, and lichenification is multiplied by the Area Score and by the Body Region Weighting to provide a body region value, which is then summed across all four body regions resulting in an EASI score as described in Equation 1 and Equation 2:

Equation 1 (subject aged 2-7 years old): $EASI = 0.2A_h(E_h + I_h + Ex_h + L_h) + 0.2A_u(E_u + I_u + Ex_u + L_u) + 0.3A_t(E_t + I_t + Ex_t + L_t) + 0.3A_l(E_l + I_l + Ex_l + L_l)$

Equation 2 (subject aged > 7 years old): $EASI = 0.1A_h(E_h + I_h + Ex_h + L_h) + 0.2A_u(E_u + I_u + Ex_u + L_u) + 0.3A_t(E_t + I_t + Ex_t + L_t) + 0.4A_l(E_l + I_l + Ex_l + L_l)$

A = Area Score; E = erythema; I = induration/papulation; Ex = excoriation; L = lichenification; h = head and neck; u = upper limbs; t = trunk; l = lower limbs

The EASI score can vary in increments of range from 0.0 to 72.0, with higher scores representing greater severity of AD. Considering the scalp will be excluded from EASI assessment in the study, the maximum possible score will be less than 72.0 (modified EASI score).

Reference:

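### EASI totals are imputed on the raw scale with no floor, so impossible negative scores can count as EASI-75 responses

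*SAP*

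**What the plan says.** SAP 5.3 sets out multiple imputation by MCMC, run separately in each arm. For ISGA, "The imputed values will be rounded to the nearest value of 0, 1, 2, 3, or 4", and the binary endpoints are derived afterwards. Missing EASI totals are "imputed in the same way as missing ISGA scores except no rounding will be done to the imputed values", and EASI-50 and EASI-75 are then derived from the completed scores. The section gives no minimum, maximum or transformation for EASI and does not list the variables in the imputation model. It names the SAS procedure that pools the results, but not the distribution used to create them.

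SAP Appendix 3.2 fixes the scale: "The EASI score can vary in increments of range from 0.0 to 72.0". A negative total therefore cannot occur.

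SAP 6.2.7 compares EASI-50 and EASI-75 between arms at Days 8, 15, 22 and 29, with MCMC multiple imputation as the only missing-data method; the table in SAP Appendix 1 agrees. For the two ISGA endpoints at Day 29, SAP 6.2.1.2 and 6.2.2.2 add non-responder imputation as a supportive analysis.

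**The concern.** An instruction to round to whole grades makes sense only if the draws are continuous, and the usual MCMC imputation model is multivariate normal. Applied to raw EASI, that model adds symmetric noise with one residual SD for every subject, whatever the baseline. In a subject with a low baseline, that SD is large relative to the score. Some draws then fall below 25% of baseline, or below 0, even when the predicted course is poor.

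At stake are the reported EASI-75 rates, risk differences and p-values. No other planned analysis of EASI-50 or EASI-75 would show that the imputation had distorted them.

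**Working it through.** **1. The plan's own figure.** Protocol 9.1: "The total sample size of 384 subjects in this study with a 2:1 randomization ratio (256:128) will provide approximately 90% power" for a "12% difference of percent change from baseline in EASI total score at Day 29 between crisaborole arm and vehicle arm". SAP 5.1 tests at two-sided 0.05. The SD is redacted, so power cannot be checked independently. Solving for it: SD = 12 / [(1.960 + 1.282) × √(1/256 + 1/128)] = 12 / (3.242 × 0.1083) = 34.2. SDs of 33, 34 and 35 give power of 91.9%, 90.3% and 88.6%. The value 34.2 is used below as an assumption. The planned means are in the documents: "The converted EASI percent improvement is 38.9% and 26.8% respectively".

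**2. The mechanism by hand, vehicle arm.** Assume that baseline EASI is lognormal with median 7 and log-SD 0.6, and that the Day 29/baseline ratio is normal with mean 1 − 0.268 = 0.732 and SD 0.342.

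- True EASI-75 rate at any baseline: Φ((0.25 − 0.732)/0.342) = Φ(−1.41) = 7.9%.
- Common residual SD on the raw scale given baseline: 0.342 × √E(b²) = 0.342 × √(49 × e^0.72) = 0.342 × 10.03 = 3.43.
- For a subject with baseline b, the imputed score is N(0.732b, 3.43²). P(negative) = Φ(−0.732b/3.43) and P(EASI-75) = Φ(−0.482b/3.43).

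| Baseline | P(negative) | P(EASI-75) imputed | True |
|---|---|---|---|
| 3.5 | 22.8% | 31.1% | 7.9% |
| 7 | 6.8% | 16.3% | 7.9% |
| 14 | 0.1% | 2.5% | 7.9% |

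The fault is the constant raw-scale SD: low baselines are credited far too often and high baselines too rarely.

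**3. Simulation at the planned means.** 36 scenarios, 200,000 subjects per arm: ratio gamma or normal clipped at 0; baseline log-SD 0.4 to 0.8; visit correlation 0.6 to 0.8; imputation from baseline alone or with visits up to Day 8 or Day 22.

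- Negative draws: 2.5-17.8%.
- Crisaborole EASI-75 among imputed subjects: 16.0-26.4% against a true 11.6-14.7%, an excess of 1.6 to 14.8 points.
- Vehicle: 9.2-22.2% against a true 3.7-8.0%, an excess of 2.1 to 18.5 points.

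The excess was positive throughout and larger on vehicle. A separate simulation with about 11% missing gave 3.5-12% negative draws, 13-20% against a true 7-10% on crisaborole, and 9-15% against a true 2-5% on vehicle.

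**4. Whole-arm size.** Shift = fraction missing × excess. The documents give no missing fraction. At 5-15% it runs from 0.05 × 1.6 = 0.08 to 0.15 × 18.5 = 2.8 points. In one mid-range scenario (clipped normal, log-SD 0.6, baseline only) the excess is 6.7 points on crisaborole and 8.6 on vehicle. At 15% missing the arms rise by 1.0 and 1.3 points, and the difference falls by 0.3.

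**5. Dependence on response level (gamma ratio).**

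| Mean improvement | True EASI-75 | Imputed EASI-75 |
|---|---|---|
| 50% | 25.2% | 26.0-28.6% |
| 60% | 41.7% | 34.8-36.6% |
| 70% | about 59% | about 45% |

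**6. Alternatives.**

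- Setting negative draws to 0 changes nothing, because 0 is still a response.
- Restricting draws to 0 or above gives 10.3-13.3% on crisaborole (true 11.6-14.7%) and 7.3-9.2% on vehicle (true 3.7-8.0%), leaving up to about 5 points of excess on vehicle under the gamma model.
- Log(EASI + constant) depends on the constant. With about 4% of scores at 0 and a true rate of 9.2%, the raw scale gave 16.4%, and constants of 1, 0.1 and 0.01 gave 12.6%, 21.7% and 30.8%. With constant 1, EASI-50 was 39.1% against a true 27.4% (raw scale 31.1%).
- Predictive mean matching on percent change came within about 0.5 point of the truth in the 11%-missing scenarios.

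**The case against.** The strongest reply is that this matters little. EASI-50 and EASI-75 are other secondary endpoints outside the SAP 5.1 testing sequence, and the primary endpoint uses MMRM without imputation (SAP 6.1.1.1). A one-arm shift of 1 or 2 points is also small beside sampling error: at 256:128 the standard error of the difference is √[p(1 − p)(1/256 + 1/128)], or 1.8 points at p = 3% and 3.5 at p = 12%. All of that stands and limits the priority. The normal model is also an inference from silence. That stands too, but a pre-specified analysis should not leave the imputation distribution to be guessed.

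Four stronger readings might be inferred, and the material does not support them.

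- **That the method favours crisaborole.** The excess arises in both arms and is usually larger on vehicle, so it tends to dilute the difference.
- **That it always inflates EASI-75.** The sign depends on the response level (step 5).
- **That poor responders are the ones credited.** The documents do not say who will have missing data.
- **That rounding normal draws also undermines the ISGA endpoints.** Rounding keeps ISGA on its scale. In simulation the Success rate moved by less than 0.5 point per arm at 5-15% missing, in a direction that depended on the score distribution and on whether baseline was in the model. Non-responder analyses are already planned, and Protocol 9.2.2 also specifies MCMC for ISGA, so changing it would set the SAP against the protocol for negligible gain.

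**Conclusion.** The point holds for EASI-75 at the planned effect sizes. As written, SAP 5.3 allows impossible EASI totals and counts every one as a response. Across the simulations, EASI-75 among imputed subjects is about 13-26% against a true 7-15% on crisaborole, and about 9-22% against a true 2-8% on vehicle. The whole-arm effect is modest, and no gated claim is touched.

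These sizes rest on assumptions that the documents do not supply: a normal imputation model, the back-solved SD of 34.2, the baseline EASI distribution, the visit correlation and the missing fraction. The simulations address Day 29; earlier visits were not examined. The correction is worth making before unblinding because it is cheap and no listed analysis would reveal the error.

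**What to change.** In SAP 5.3, replace the EASI sentence with a stated model: predictive mean matching, run by arm, preferably on percent change from baseline, with baseline EASI and earlier visits as predictors and the number of donors given. Imputed values then stay within the range actually observed. Derive EASI-50 and EASI-75 from the completed data as now. State that negative draws are not to be handled by setting them to 0, and do not adopt a log transformation with an unspecified constant.

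In SAP 6.2.7 and the Appendix 1 table, add non-responder imputation as a supportive analysis for EASI-50 and EASI-75, as already done for ISGA. Leave the ISGA imputation unchanged.

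The cost is SAP wording and a different imputation statement in the program, with no new data. Protocol 9.2.3 names no missing-data method for EASI-50 or EASI-75, so the change does not contradict the protocol.
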